Study Design: This study is a pilot phase 1 study of patients with moderately to severely active Crohn Disease (CD) and ulcerative colitis (UC) (≥ 18 years, Mayo score: ≥ 6 or CDAI: > 220 ; < 18 years, Pediatric Crohn's Disease Activity Index (PCDAI) > 30) or Pediatric Ulcerative Colitis Activity Index (PUCAI) > 34). [1] [2] A fixed dose will be studied: 1×10^6 cells/kg administered intravenously (IV) weekly for 4 consecutive weeks, with the option of an additional 4 weeks of treatment, at the discretion of the principal investigator. The primary outcomes are regimen-related toxicity, defined in section 5. Toxicity will be scored as a binary variable indicating occurrence or non-occurrence over a monitoring interval from the start of MSC therapy to 45 days after the last infusion. Based on the planned administration schedule of 4 weeks, the total toxicity monitoring period will have duration $28 + 45 = 73$ days. If additional weekly doses are administered, the safety assessment phase will be 45 days after the last dose given.

Three young adult patients (ages 17≤22 years) will be enrolled, staggered by at least 7 days, and monitored for toxicity over a period of 73 days. Infusions are administered over the first 28 days, followed by a 45 day monitoring period. If we observe no severe (grade 3 or worse) adverse events in the young adult cohort, we will wait a minimum of 45 days after the last MSC administration before beginning to enroll 3 more patients, ages 12≤16 (pediatric cohort). If we observe a severe (grade 3 or worse) adverse event occurring at any time from the start of therapy to 45 days following the last MSC administration in the young adult cohort we will stop the study. If we observe no severe adverse events attributable to MSCs in the young adult cohort but a severe (grade 3 or worse) adverse event occurring at any time from the start of therapy to 45 days following the last MSC administration in the pediatric cohort we will stop the study. A maximum of 6 patients will be enrolled. Assuming an accrual rate of 3-4 patients per year, it is anticipated that it will require at least 18-24 months to accrue all 6 patients.

Eligibility

This protocol allows for the treatment of both male and female pediatric and young adult patients, between the ages of 12 ≤ 22 years, with active moderate to severe CD or UC, who have failed to respond to, or are intolerant of, biologic therapy.

Inclusion criteria

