3 STUDY AGENT

3.1 Preparation Administration, and Dosage

On the day of each infusion, the following procedures/assessments will be performed:

- MSCs will be thawed, harvested, counted, the viability will be determined, and appropriate samples will be sent for other release testing (including sterility). Vital signs (heart rate, blood pressure, respiratory rate, and temperature) will be measured within 15 minutes prior to the infusion (time 0) and then every 5 minutes during the infusion. If vital signs are normal after three 5-minute checks, they will be checked every 15 minutes during the remainder of the infusion, and then at 30 and 60 minutes after the infusion for 1 hour.
- Patients will be monitored according to institutional standards for administration of blood products and at a minimum will be monitored according to below:
 - Patients should remain in the clinic for at least one hour
 - Patients should remain on continuous pulse oximetry for at least 30 minutes

- Vital signs should be monitored at the end of the infusion then at 30 and 60 minutes
- Per institutional guidelines, pre-medication, consisting of oral acetaminophen (10-15 mg/kg/dose, max 650 mg) and diphenhydramine (0.5-1 mg/kg/dose, max 50 mg), will be administered at least 30 minutes prior to the infusion.
- No other medications should be given during the infusion, unless determined medically necessary by the treating physician.
- Supplemental oxygen will be kept by the bedside at all times.
- MSCs suspended in Plasmalyte A (multiple electrolyte injection) will be given as an IV infusion using weight-based dosing. We plan to infuse $1-4 \times 10^6$ cells per mL, not to exceed 240 mL. With a mean weight of 40 kg, the infusion volume would be 40-120 mL.
- Cells will be infused on Day 0 followed by repeat infusions weekly over a total of 4 weeks. An additional 4 weekly doses may be infused at discretion of physician. An attempt will be made to administer repeat infusions from the same initial donor, but administration of MSCs from another donor is permitted if same-donor cells are unavailable. Tracking of donor sample identification information will be performed for each sample.

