- MSC's will be administered intravenously via a 18 gauge needle at a controlled rate of 4-6 ml/minute via infusion pump for patients weighting 35 kg or more. For patients under 35 kg in weight, the infusion will run in over 60 minutes at a rate no greater than 4-6 ml/minute. A syringe in combination with syringe pump can be used for administration in smaller patients.
- During the administration, the infusion must be stopped for any of the following reasons:
 - If the patient has symptoms or signs of respiratory difficulty, including but not limited to tachypnea, cyanosis, complains of shortness of breath, even if the pulse oximeter reading is normal. If the symptoms resolve within 30 minutes after standard supportive oxygen therapy, the infusion may be resumed at half the initial rate and the infusion must be completed within 2 hours of starting the infusion. If the symptoms recur, then the infusion will be stopped and will not be resumed.
 - If SaO_2 decreases to $\leq 90\%$ over a continuous period of > 3 minutes, whether or not the patient has symptoms of respiratory distress. If the SaO_2 is $\leq 90\%$ in the absence of symptoms or signs, the accuracy of the pulse oximeter reading should be confirmed by using another machine, relocating the sensor, or testing the device on another patient.
 - Infusion may be stopped at the discretion of the treating physician if there is another AE that the treating physician believes is related to the infusion, or if there is an issue with the infusion, or if the patient withdraws consent.

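### Protocol Section 3.1 contradicts itself on infusion volume: at the fixed dose and planned concentration a 40 kg patient needs 10–40 mL, not the printed 40–120 mL

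*Protocol*

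**What the plan says.** The dose is set in the synopsis (Study Design): "A fixed dose will be studied: 1×10^6 cells/kg administered intravenously (IV) weekly for 4 consecutive weeks". Sections 1.4.2, 1.4.3 and 2.2 repeat it, and Section 1.4.2 gives the same cell number for any optional extra doses.

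Section 3.1 covers preparation and refers only to weight-based dosing. It plans 1–4×10^6 "cells per mL, not to exceed 240 mL", and the next sentence gives the worked volume: "With a mean weight of 40 kg, the infusion volume would be 40-120 mL".

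The rate in the same section depends on weight. Patients of 35 kg or more are infused "at a controlled rate of 4-6 ml/minute via infusion pump for patients weighting 35 kg or more", with no minimum duration. For lighter patients, "For patients under 35 kg in weight, the infusion will run in over 60 minutes at a rate no greater than 4-6 ml/minute".

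One mandatory stop in Section 3.1 is timed: oxygen saturation of 90% or less "over a continuous period of > 3 minutes, whether or not the patient has symptoms of respiratory distress".

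**The concern.** Dose, weight and concentration determine volume, and Section 3.1 supplies concentration and volume in adjacent sentences. If they disagree, whoever prepares the product cannot follow both. At 40 kg, one instruction leads to 10 mL of suspension and the other to as much as 120 mL.

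Safety and tolerability is the primary objective, and the volume and duration of the infusion are part of what is being tolerated. Volume divided by rate also gives the duration, so the choice of range decides whether the timed saturation stop can act during the infusion.

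**Working it through.** **Inputs**
- Dose: 1×10^6 cells/kg (synopsis; Sections 1.4.2, 1.4.3, 2.2).
- Concentration: 1–4×10^6 cells/mL (Section 3.1).
- Weight in the protocol's own example: 40 kg (Section 3.1).
- Printed volume: 40–120 mL, with a ceiling of 240 mL (Section 3.1).
- Rate at 35 kg or more: 4–6 mL/min (Section 3.1).

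**Attempt to reproduce the printed volume**

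Volume (mL) = dose per kg × weight / concentration.
- Cells at 40 kg: 1×10^6 × 40 = 40×10^6.
- At 4×10^6/mL: 40/4 = 10 mL.
- At 1×10^6/mL: 40/1 = 40 mL.

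The result is 10–40 mL, so 40–120 mL is not reproduced. The lower ends differ by 40/10 = 4 and the upper ends by 120/40 = 3.

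**What the printed volume would imply**
- Concentration at the fixed dose: 40/120 = 0.33 to 40/40 = 1.0 (×10^6/mL). All of this lies below the stated minimum except the single point of 40 mL.
- Dose, if the concentration range is right: 40 mL at 4×10^6/mL is 160×10^6 cells, or 4×10^6/kg. 120 mL at 1×10^6/mL is 120×10^6 cells, or 3×10^6/kg. The two ends need different doses.

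The second result can be seen without any dose. At a fixed dose and weight, a fourfold concentration range must give a fourfold volume range. The printed range is threefold (120/40), so no single dose reconciles the two sentences.

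**Does the 240 mL ceiling decide which is wrong?**
- At 1×10^6/mL the ceiling is reached at 240 × 1 = 240 kg, and at 4×10^6/mL at 240 × 4 = 960 kg. It never binds.
- At 0.33×10^6/mL it is reached at 240/3 = 80 kg.

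The ceiling has a practical role only under the lower concentrations. That does not prove that they were intended.

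**Duration at 40 kg** (volume / rate)

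| Basis | Volume | Shortest | Longest |
|---|---|---|---|
| Dose and concentration | 10–40 mL | 10/6 = 1.7 min | 40/4 = 10 min |
| Printed volume | 40–120 mL | 40/6 = 6.7 min | 120/4 = 30 min |
| Only point common to both | 40 mL | 40/6 = 6.7 min | 40/4 = 10 min |

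**When the saturation stop could not be met**

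An infusion lasts 3 minutes or less when the concentration is at or above weight/(3 × rate). At 40 kg this is 40/18 = 2.22×10^6/mL at 6 mL/min, and 40/12 = 3.33×10^6/mL at 4 mL/min. This arises only if the 1–4×10^6/mL range is the one kept. Under the printed volume the shortest infusion is 6.7 minutes.

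**The case against.** The strongest reply is that the dose is stated consistently throughout and the 40 kg sentence is only an illustration. That much stands. A reader might infer that patients could receive the wrong number of cells, but the documents do not support it: the cell number follows from weight and the fixed dose, whichever volume is used.

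A reader might also infer that Section 3.1 lets the infusion outrun its monitoring, and that patients of 35 kg or more therefore need a minimum infusion time or a slower rate. The documents do not carry this, for four reasons.
- It depends on which range is wrong, and that is not shown. The one reading that satisfies both sentences gives 6.7–10 minutes.
- Vital signs are also required at the end of the infusion, so one that finishes before the first 5-minute check still gets a check, and an earlier one. The condition "If vital signs are normal after three 5-minute checks, they will be checked every 15 minutes during the remainder of the infusion" governs when the frequency may be relaxed. It does not require three checks within every infusion.
- A separate mandatory stop covers symptoms or signs of respiratory difficulty with no time requirement, even when the oximeter reads normal. What lies outside a mandatory stop is desaturation with neither symptom nor sign, in a very short infusion. Any rule that needs more than 3 sustained minutes also misses desaturation beginning in the last 3 minutes, however long the infusion.
- Sections 1.4.2 and 1.4.3 support the weight-split rate scheme as consistent with earlier paediatric use in graft-versus-host disease. Overriding it would be a debatable trade-off and not the correction of an error.

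Monitoring also continues after a short infusion: "Patients should remain on continuous pulse oximetry for at least 30 minutes", vital signs follow at 30 and 60 minutes, and the physician may stop for another related adverse event without waiting 3 minutes.

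None of this reconciles 40–120 mL with 1–4×10^6 cells/mL.

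**Conclusion.** Wrong as written; minor to moderate severity. At the protocol's own dose, weight and concentration the volume is 10–40 mL, and the printed 40–120 mL agrees with it only at 40 mL. This is arithmetic on the protocol's figures as printed and needs no outside source.

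The effect on the saturation stop is conditional. It arises only if 1–4×10^6/mL is the intended range, and at 40 kg only from 2.22×10^6/mL (6 mL/min) or 3.33×10^6/mL (4 mL/min) upward. Even then, what may be lost is one written rule's power to interrupt the dose, not the detection of desaturation. The concentration actually used and the patients' weights are not given, so the share of infusions affected is unknown.

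**What to change.** Amend Section 3.1 so that volume and concentration agree, in one of two ways:
- keep 1–4×10^6 cells/mL and print 10–40 mL at 40 kg; or
- keep 40–120 mL at 40 kg and print 0.33–1.0×10^6 cells/mL. Add that above 80 kg the concentration must exceed 0.33×10^6/mL to stay within 240 mL (minimum, in 10^6/mL, = weight in kg / 240).

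If the first is chosen, check that the rule for more than 3 minutes of low saturation suits an infusion of 1.7–10 minutes at 40 kg. One simple answer is to limit the concentration to about 1×10^6/mL, which gives 6.7–10 minutes at 40 kg and leaves the 4–6 mL/min rate unchanged.

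The cost is a text amendment and the matching change to any preparation worksheet. It needs no extra patients, visits or procedures. With the concentration limit, a 40 kg patient would receive 40 mL instead of as little as 10 mL. The infusion would run at most 5.0 minutes longer at 6 mL/min (6.7 − 1.7) or 7.5 minutes longer at 4 mL/min (10 − 2.5).

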Our cell therapy product consists of allogeneic mesenchymal stromal cells manufactured from an eligible normal donor. We have a CNMC IRB-approved protocol (Pro00006717) that provides a mechanism for the use of excess bone marrow obtained from healthy donor bone marrow harvests. Up to 100 mL of marrow will be obtained from Lonza (Walkersville, MD) under informed consent and transported to Children's National Health System in a validated process at 2-8°C. The donor will meet the eligibility requirements as described in 21 CFR parts 1271 Subpart C. Testing (Table 1) will be performed using FDA-approved, cleared and/or licensed kits by Lonza within 7 days of collection of the marrow for manufacturing. Manufacturing will commence within 24 hours of marrow collection. Risk factors will be assessed by taking a clinical history, clinical examination, and by use of a standard questionnaire for blood donors.

Table 1:	Test
Chagas Disease	
Hepatitis B Surface Antigen	
Hepatitis B Core	
Hepatitis C Core	
HIV 1 and 2	
TAQ Screen MPX (HBV, HCV, HIV-1 group M RNA, HIV-1 Group O)	
NAT HCV	
NAT West Nile Virus	
Serological Test for Syphilis	
CMV	
HTLV-1	

This would not be a first-in-human study and there is now a sizable body of evidence that this intervention is safe when used in people ≥ 18 years of age. However, the safety of MSCs has not been yet demonstrated in

children with IBD. Safety and dosing may not be extrapolated from adult studies, as classic pharmacokinetic monitoring to document equivalent exposure-response is not feasible with cell therapies.

1.4.2 PLAN OF STUDY:

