In our study, toxicity will be scored as a binary variable indicating occurrence or non-occurrence over a monitoring interval from the start of MSC therapy to 45 days after the last infusion. Based on the planned administration schedule, the total toxicity monitoring period will have duration $28 + 45 = 73$ days. If we observe no severe (grade 3 or worse) adverse events in the young adult cohort, we will wait a minimum of 45 days before beginning to enroll 3 more patients, ages $12 \leq 16$ years (pediatric cohort). If we observe a severe (grade 3 or worse) adverse event occurring at any time from the start of therapy to 45 days following the last MSC administration in the young adult cohort we will stop the study. If we observe no SAEs attributed to MSC administration in the young adult cohort but an SAE (grade 3 or worse) occurring at any time from the start of therapy to 45 days following the last MSC administration in the pediatric cohort, we will stop the study. If patients with active disease do not have >grade 2 toxicity attributed to

cells and fail to rapidly progress with disease requiring urgent therapy or surgery, and at the discretion of the principal investigator, 4 additional weekly doses may be administered. Subjects are eligible to receive up to 4 additional doses of MSCs at weekly intervals, each of which will consist of the same cell number (1×10^6 cells/kg). The safety assessment period will be 45 days from the last dose administered. A maximum of 6 patients will be enrolled. Assuming an accrual rate of 3-4 patients per year, it is anticipated that it may require at least 18- 24 months to accrue all 6 patients. With the additional 24 months of follow up to evaluate longer-term safety and efficacy endpoints, the anticipated trial duration will be about 48 months.

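### The rule for optional doses 5 to 8 is stated in three conflicting ways, and opening the pediatric cohort does not depend on how many doses the young adults received

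*Protocol*

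**What the plan says.** The option of a second block of infusions appears in three places in the Protocol.

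- **Synopsis, Study Design:** the 4-week course is given "with the option of an additional 4 weeks of treatment, at the discretion of the principal investigator". No condition on disease or toxicity is attached.
- **Section 1.4.2, Plan of Study:** the option opens with "If patients with active disease do not have >grade 2 toxicity attributed to" the cells, continues with the requirement that they "fail to rapidly progress with disease requiring urgent therapy or surgery", and ends with "at the discretion of the principal investigator, 4 additional weekly doses may be administered". It then adds: "Subjects are eligible to receive up to 4 additional doses of MSCs at weekly intervals". No cohort is excluded.
- **Section 3.1, Preparation, Administration and Dosage:** "An additional 4 weekly doses may be infused at discretion of physician". There is no condition, and the principal investigator is not named.

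On staging, the synopsis says that if the young adults have no severe event, "we will wait a minimum of 45 days after the last MSC administration before beginning to enroll 3 more patients". Sections 1.4.2, 2.2 and 7.1.4 rest on the same test of no severe event among the three young adults. Section 1.4.2 says the order of cohorts was specified in the FDA IND review, and section 1.4.1 gives a reason for caution: "Safety and dosing may not be extrapolated from adult studies".

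Section 2.2, Table 1 and section 3.8 describe 4 infusions only. The pregnancy-test criterion in section 2.6.2 is likewise written for 4 infusion visits.

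**The concern.** The three statements differ on who decides and on which patients qualify. The least restrictive of them sits in the section that staff will have open when they infuse. The difference is unlikely to be mere shorthand: section 3.1 elsewhere uses the term treating physician, and section 2.2 gives that role standard of care and the management of toxicity, so a reader of section 3.1 need not take the physician to be the principal investigator.

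The second issue is exposure. The cohorts are ordered by age so that the children follow observed experience in young adults. The protocol never says whether this order also applies to the extended course. Since safety and tolerability are the only primary aim, and at most six patients are treated, it matters who may receive up to 8 infusions, on what terms, and with what scheduled safety observation.

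**Working it through.** **1. The three statements side by side**

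| | Synopsis | Section 1.4.2 | Section 3.1 |
|---|---|---|---|
| Decision-maker | principal investigator | principal investigator | physician |
| Active disease required | no | yes | no |
| No toxicity above grade 2 attributed to cells | not stated | required | not stated |
| No rapid progression | not stated | required | not stated |

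Two of the three lack every condition, and one differs on the decision-maker.

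**2. What other sections cover if section 3.1 is followed**

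- *Toxicity.* Above grade 2 means grade 3 or worse. Under section 7.1.4 one such event in either cohort stops the study. Section 5.6 ends study treatment after a grade 3 or 4 infusion reaction. A gap remains if the stop is read through that section's own definition of toxicity (probable or definite relation): a grade 3 event rated only possible might then not stop the study.
- *Progression.* Section 6 lists worsening (PCDAI above 50 or PUCAI above 65) and rescue treatment, but as grounds on which a subject may be withdrawn, and with thresholds on the pediatric indices only. Cover is partial.
- *Active disease at the time of dose 5.* No other section requires it.

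**3. Dose and window**

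Inputs: 1×10^6 cells/kg per infusion; doses on Days 0, 7, 14 and 21 (Table 1); window to 45 days after the last dose (synopsis, section 1.4.2). Assumption: weekly dosing runs on after dose 4 without a break, so dose k falls on Day 7(k − 1).

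- The plan's own figure: 28 + 45 = 73 days. This reproduces. It counts four full weeks, that is 7k + 45 with k = 4.
- Counted strictly from dose 4: 21 + 45 = Day 66.
- With 8 doses, the last is on Day 7 × 7 = 49. Strict count: 49 + 45 = Day 94. Protocol convention: 7 × 8 + 45 = Day 101.
- Beyond the Day 73 visit: 94 − 73 = 21 days, or 101 − 73 = 28 days. Day 73 is the last visit with an AE/SAE mark in Table 1; the next visit is Day 180.
- Cumulative dose: 4 × 10^6 against 8 × 10^6 cells/kg, a ratio of 2.

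**4. Can a child be the first to go beyond 4 doses?**

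The number of young adults required to have had more than 4 doses before a child may is 0 of 3. How often this would happen depends on uptake, which the protocol does not give. Assume that each patient takes the option independently with probability q, that no severe event occurs and that all six are treated:

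- P(no young adult beyond 4) = (1 − q)^3
- P(no young adult, at least one child) = (1 − q)^3 × [1 − (1 − q)^3]

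| q | no young adult | no young adult, at least one child |
|---|---|---|
| 10% | 73% | 20% |
| 25% | 42% | 24% |
| 50% | 13% | 11% |
| 75% | 2% | 2% |

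**The case against.** The strongest reply is that the protocol is safer than section 3.1 read alone. A reader might infer from that section that a patient with attributed toxicity above grade 2 could simply continue. The study stop and the infusion-reaction rules block most of that, so this reading is not supported beyond the narrow gap in step 2.

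A reader might also infer that the option bypasses the young-adult-first design. It does not. No child enrolls until the young adults have cleared the condition. The staging is by age at one fixed dose per infusion, and no section says that it was meant to stage the number of doses. What stands is that the extended exposure is unstaged and that the protocol is silent on whether this is intended.

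Third, sections 1.4.2 and 1.4.3 cite pediatric GvHD use of up to 8×10^6 cells/kg per dose, up to twice weekly for four weeks: 8 infusions and 8 × 8×10^6 = 64×10^6 cells/kg. So 8×10^6 cells/kg in total is not extreme against the protocol's own precedent. But that precedent ran over 4 weeks in another disease, it is offered in support of the 4-week course, and section 1.4.2 itself declines to extrapolate safety and dosing from other populations.

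Fourth, the variable window is defined, and section 8 requires doses and dates to be recorded, so any count of toxicities can be reported with infusions received. This is right. The endpoint is not undefined, and detailed tabulation may sit in a statistical analysis plan that is not shown. The mismatch between the extended window and Table 1 remains. Section 3.8 permits telephone screening for adverse events in follow-up, but the first such contact is Day 180.

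Finally, extending the staging would give little statistical assurance: even with all three young adults on extended courses, 0 of 3 events leaves a one-sided 95% upper limit of 1 − 0.05^(1/3) = 63%. That is true of the base course too, and is no reason to leave the rule unstated.

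**Conclusion.** The point holds as a contradiction in the protocol's text and should be corrected. Section 3.1 and the synopsis omit all three conditions found in section 1.4.2, and section 3.1 also changes the decision-maker. The practical loss is the active-disease condition, much of the progression condition and a named decision-maker, with a small residual gap on toxicity.

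Separately, up to 8 infusions are open to a child when no young adult has had more than 4, while enrollment itself stays staged. The size is a doubling of cumulative dose and 21 to 28 days of safety window after the last marked AE/SAE visit. Those day counts assume no pause between doses 4 and 5; a pause would push the end of the window later. The chance that a child goes first, 2% to 24%, rests wholly on assumed uptake of 10% to 75% and independence between patients, and is illustrative only.

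The documents do not show that the staging as a whole fails, or that patients with severe attributed toxicity would routinely continue. Which clinical rule is right is for the sponsor to decide.

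**What to change.** 1. Reconcile the synopsis, section 1.4.2 and section 3.1 into one rule with one decision-maker and one set of conditions, and refer to it from the other places.
2. Have the sponsor and the DRC state whether the young-adult-first order also governs doses 5 to 8. Either answer removes the ambiguity.
3. Align Table 1 and section 3.8 with the extended course: add the further infusion visits and AE/SAE assessment up to the end of the 45-day window, state whether that end is counted from the last dose or by the 28 + 45 convention, and reconcile the pregnancy-test wording, which mentions only 4 infusion visits.
4. Report toxicity by cohort with the number of infusions each patient received. Do not close the 4-dose window at dose 5: patients who continue would then have 28 days of observation against 66 for those who stop, and late toxicity from the first course would be counted against the second.

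The cost is protocol wording, some schedule columns and one column in a table of at most six patients. Depending on the answer to item 2, fewer children might receive an extended course.
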